4.3 Exclusion Criteria

Subjects meeting ANY of the following criteria must NOT be enrolled in this study:

1. Has had prior exposure to tazemetostat or other inhibitor(s) of EZH2.
2. Is being actively treated for another concurrent malignancy or is less than 5 years from completion of treatment for another malignancy.
3. Has participated in another interventional clinical study and received investigational drug within 30 days or five half-lives, whichever is longer, prior to the planned first dose of tazemetostat.
4. Has had major surgery within 2 weeks prior to enrollment.
NOTE: Minor surgery (e.g., minor biopsy of extracranial site, central venous catheter placement, shunt revision) is permitted within 2 weeks prior to enrollment.
5. Has thrombocytopenia, neutropenia, or anemia of Grade ≥ 3 (per CTCAE 4.03 criteria) or any prior history of myeloid malignancies, including myelodysplastic syndrome (MDS). Has abnormalities known to be associated with MDS (e.g. del 5q, chr 7 abn) and MPN (e.g. JAK2 V617F) observed in cytogenetic testing and DNA sequencing.
NOTE: Bone marrow aspirate/biopsy will be conducted following abnormal peripheral blood smear morphology assessment at Screening. Cytogenetic testing and DNA sequencing will be conducted by a central laboratory following an abnormal result of bone marrow aspirate/biopsy.
6. Has a prior history of CCI/T-ALL.
7. Has clinically active heart disease including prolonged QTcF (>450 msec).
8. Is currently taking any prohibited medication(s) as described in Section 7.3.

9. Is unwilling to exclude grapefruit juice, Seville oranges and grapefruit from the diet and all foods that contain those fruits from time of enrollment to while on study.
10. Has an active infection requiring systemic treatment.
11. Is immunocompromised (ie, congenital immunodeficiency), including subjects with a known history of infection with human immunodeficiency virus (HIV).
12. Has known history of chronic infection with hepatitis B virus (hepatitis B surface antigen positive) or hepatitis C virus (detectable HCV RNA).
13. Has had a symptomatic venous thrombosis within 14 days prior to study enrollment.
NOTE: Subjects with a history of a deep vein thrombosis 14 days prior to study enrollment who are on anticoagulation therapy with low molecular weight heparin are eligible for this study.

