6.5.1 Dose Modification due to Toxicity Not Related to Bromide

Other toxicities that, in the opinion of the Investigator are possible, probably, or definitely related to study treatment, should be managed per [Table 5](#). Toxicities that are felt by the Investigator to be unrelated to tazemetostat but clinically significant should be discussed with the Medical Monitor. In the event of an urgent unrelated toxicity, study treatment should be interrupted as per [Table 5](#). Dose re-escalation is not permitted.

Table 7. Dose Modifications for Treatment-Related Toxicities (Other than Toxicities Related to Bromide)

Toxicity ^a	During Therapy	Dose Adjustment ^{b,d}
Grade 1		
All occurrences	Continue study treatment	Maintain dose level
Grade 2		
All occurrences	Continue study treatment	Maintain dose level
Grade 3^c (not including neutropenia)		
1st occurrence	Interrupt study treatment until resolved to Grade ≤1 or baseline ^b	Reduce by one dose level
2nd occurrence (same or new toxicity)		Reduce by two dose levels
3rd occurrence (same or new toxicity)	Discontinue study treatment	Not applicable
Grade 3 neutropenia (ANC: <1 – 0.5 × 10⁹/L)		
1st occurrence	Interrupt study treatment until resolved to ANC ≥1.0 × 10 ⁹ /L	Maintain dose level
2 nd occurrence		Reduce by one dose level
3rd occurrence		Reduce by two dose levels
4th occurrence	Discontinue study treatment	Not applicable
Grade 4		
All occurrences	Interrupt study treatment until resolved to Grade ≤1 or baseline and discuss with Medical Monitor	Pending discussion with Medical Monitor

Abbreviations: ANC= absolute neutrophil count, BID= twice daily

- a. Excluding alopecia and nausea, vomiting or diarrhea not receiving adequate treatment.
- b. A delay of tazemetostat for more than 14 days due to any toxicity must be discussed with the Medical Monitor before treatment can be resumed.
- c. Exclude Grades 2 and 3 anemia: Subjects are allowed to continue tazemetostat at their current dose level.
- d. If more than 2 dose modifications are required, contact Medical Monitor to discuss risk:benefit ratio of continuing on study.

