6.7 Continuation of Treatment

In subjects who do not have evidence of clinical or radiographic disease progression and who do not experience unacceptable toxicity, additional cycles of tazemetostat beyond Cycle 1 may be given at the Investigator's discretion with the subject's or his/her legal representative consent.

Prior to declaring progressive disease, the Investigator should be certain that special circumstances on progression defined by RECIST 1.1 are not met. In these situations of equivocal findings of progression, subjects may continue treatment until the next scheduled disease assessment. If progression is confirmed, the date of the previous assessment will be used as the date of disease progression.

The required hematologic parameters for continuation of treatment for the second and subsequent cycles are the following:

- Platelet count must be $\geq 50 \times 10^9/L$
- ANC $\geq 1.0 \times 10^9/L$, and
- Any Grade 3 or higher toxicity must have resolved to Grade 1 or baseline

Study treatment may be interrupted for up to 14 days. Treatment interruptions longer than 14 days need Medical Monitor approval to proceed.

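### Protocol Section 6.7 holds the next cycle for Grade 3 anemia, while Table 7 footnote c lets the same child continue at the current dose

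*Protocol*

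**What the plan says.** Protocol Section 6.7 introduces its list with "The required hematologic parameters for continuation of treatment for the second and subsequent cycles are the following". Three conditions must all be met: platelets of at least 50 × 10⁹/L, ANC of at least 1.0 × 10⁹/L, and "Any Grade 3 or higher toxicity must have resolved to Grade 1 or baseline". No toxicity is exempted and Table 7 is not mentioned. The section also limits interruptions to 14 days unless the Medical Monitor approves a longer one.

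Table 7 in Section 6.5.1 governs treatment-related toxicities other than those due to bromide. Its general Grade 3 rule uses the same recovery level as Section 6.7: "Interrupt study treatment until resolved to Grade ≤1 or baseline". It then departs from that rule twice:

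- **Anemia**, in footnote c: "Exclude Grades 2 and 3 anemia: Subjects are allowed to continue tazemetostat at their current dose level".
- **Neutropenia**, in a separate row that begins "Grade 3 neutropenia (ANC: <1 – 0.5" and gives the recovery rule "Interrupt study treatment until resolved to ANC ≥1.0" × 10⁹/L.

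Two other provisions bear on the point. Section 4.3, criterion 5, which begins "Has thrombocytopenia, neutropenia, or anemia of Grade", bars entry with any of these at Grade 3 or above. Section 6.5 allows no dose modification for subjects who start expansion at 520 mg/m² BID. They may be interrupted for up to 14 days, and must come off treatment if the adverse event has not resolved by then.

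**The concern.** The two sections give opposite instructions for one finding. A site that works from Table 7 keeps dosing through Grade 3 anemia; a site that works from Section 6.7 stops at the next cycle start. The first matter at stake is the child's treatment, particularly at 520 mg/m², where an unresolved hold leads to discontinuation. The second is interpretation. The SAP summarizes TEAEs leading to interruption and to discontinuation (Section 17.1), average dose intensity (14.1) and compliance (14.2), and it makes study drug compliance a predefined category of major deviation (Section 10). Part of the variation in those outputs could come from which passage a site followed.

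**Working it through.** The plan states no figure here to reproduce. The check is a comparison of the rules, followed by one illustration of what a hold does to the SAP's own formula.

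**Rules on Day 1 of Cycle 2 or later**

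| Finding | Table 7 | Section 6.7, ANC condition | Section 6.7, toxicity condition |
|---|---|---|---|
| Treatment-related Grade 3 anemia | Continue at current dose | Not relevant | Hold to Grade 1 or baseline |
| After Grade 3 neutropenia, ANC now 1.0 × 10⁹/L | Resume | Met | Hold to Grade 1 or baseline, if the condition covers neutropenia |

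**Anemia**

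1. *Can baseline status rescue it?* No. Grade 3 or higher anemia is excluded at entry, so current Grade 3 anemia is never the child's baseline grade.
2. *Does the toxicity condition reach anemia?* Read literally, yes. It covers any toxicity, it sits in a list introduced as hematologic, and that list has no hemoglobin condition of its own.
3. *Do the scopes differ enough to separate them?* No. Table 7 covers treatment-related events and Section 6.7 covers all events, so a treatment-related anemia falls under both. Section 1.6.5 lists anemia as an adverse reaction to tazemetostat. Dosing runs in continuous 28-day cycles, with hematology scheduled on Day 1 of each (Table 11), so both rules apply on that day.
4. *Is precedence stated?* No. Neither section cites the other.

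**Neutropenia**

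Table 7 places Grade 3 at ANC below 1.0, so 1.0 is the first value outside Grade 3 and therefore falls in Grade 2. Table 7 and the ANC condition of Section 6.7 both permit treatment there. The toxicity condition would not, unless the child's baseline was already that low, which the entry limit of ANC 1.0 × 10⁹/L allows. The documents do not print the boundary between Grades 1 and 2, so how far above 1.0 the disagreement extends cannot be fixed from them.

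**Effect of a hold on dose intensity (illustration)**

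SAP 14.1 divides total drug taken by 2 × duration of exposure for BID dosing, and does not shorten the duration for interruptions. Assume a constant dose d mg BID, a 14-day hold from Day 29, full dosing on all other days, and a last dose on Day 56.

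- Days dosed: 56 − 14 = 42
- Total taken: 2 × d × 42
- Average dose intensity: (2 × d × 42) / (2 × 56) = 0.75d
- Compliance under SAP 14.2: 75%, in the 70% to <80% category

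The same child treated under footnote c would show 100%, in the ≥90% category. Longer exposure dilutes the difference.

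**The case against.** The best defense is that Table 7 is the specific rule on toxicity and Section 6.7 a general check, so footnote c should govern. But Section 6.7 is equally specific to cycle start, and the text does not rank the two. Section 15.5 sends sites to the Medical Monitor for clarification. That offers a route to an answer but does not supply a common rule.

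On neutropenia the defense is stronger. If the toxicity condition already covered neutrophils, the separate ANC condition would add almost nothing. Read as the governing neutrophil rule, the ANC condition matches Table 7 exactly. A reader might infer that Section 6.7 flatly contradicts itself, but this reading is coherent, so the point is an ambiguity of scope.

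Other strong inferences also fail:

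- *An open-ended hold.* Section 6.7 caps interruption at 14 days without Medical Monitor approval, and Section 6.5 sets a 14-day limit for subjects starting at 520 mg/m².
- *A common problem.* Section 1.6.5 reports anemia among TEAEs in at least 10% of children, and anemia and neutropenia among nonserious reactions in at least 2%. None of these is a Grade 3 rate. Its list of the commonest TEAEs that interrupted dosing has neutropenia at 2% and does not name anemia. That fits either few Grade 3 anemias or sites already following footnote c.
- *Recurrence at every cycle.* Two years hold 730 / 28 = 26.1 cycles, hence about 25 starts after Cycle 1. That is a ceiling: under Section 6.5.3 subjects with stable disease stop at one year, responders reduce or stop one year after first response, and the conflict needs an unresolved Grade 3 event on the day.
- *Sites misled by the references to Table 5 in Section 6.5.1.* Table 5 is the Rolling 6 table, but Table 7 stands directly below that text under a plain title. This is a cross-reference slip.

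**Conclusion.** The anemia conflict is established from the protocol's own words. It rests on reading the toxicity condition of Section 6.7 literally and on the anemia being treatment-related; it needs no hemoglobin cut-off. For an affected child, the difference runs from no interruption to a hold of up to 14 days, beyond which Medical Monitor approval is needed. For a subject starting at 520 mg/m², an event that does not resolve with interruption requires discontinuation. The number of such children cannot be derived from the documents.

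The neutropenia point is secondary and conditional on what the toxicity condition is meant to cover.

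The consequences are for safety conduct and for descriptive summaries. A reader might infer that the efficacy decision or dose finding is compromised; the documents do not support that. The definition of ORR and the 3-of-20 threshold do not refer to these rules. DLTs are confined to Cycle 1, whereas Section 6.7 applies its conditions from Cycle 2. The defect still warrants correction, because it gives opposite treat and hold instructions and costs little to remove.

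**What to change.** Reconcile Section 6.7 with Table 7, so that each toxicity has one recovery rule in both places:

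- State in Section 6.7 whether the anemia exemption and the ANC 1.0 × 10⁹/L recovery threshold of Table 7 apply at cycle start.
- State what the toxicity condition covers: all toxicities, only those without their own rule, or only non-hematologic ones.
- Check the Section 6.5 list of Grade 3 or higher non-hematologic toxicities that need no dose modification against the same condition. Its entries for transient fatigue or asthenia and transient myalgia or arthralgia give no recovery grade.
- Correct the two references to Table 5 in Section 6.5.1.

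Which clinical rule applies is for the sponsor's clinicians to decide. The cost is a short wording change in an amendment or clarification letter, with no added procedures and no change to the sample size. If subjects have already been treated under the current wording, the CSR should say that sites may have applied either rule when it presents interruptions, discontinuations and dose intensity.

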6.8 Duration of Tazemetostat Treatment

Treatment with tazemetostat will continue until disease progression or unacceptable toxicity, for a maximum of 2 years either cumulatively or consecutively, see Section 5.3 for details.

6.9 Treatment Compliance

Compliance for doses taken outside of the clinic may be assessed by the return of study drug to the study site and review of doses taken with the subject (or guardian). This will be recorded in the source documents, which may include the use of a subject medication diary per institutional practice.

6.10 Treatment of Overdose

In the event of an overdose of tazemetostat (defined as administration of more than the protocol-specified dose), the Investigator should contact the Medical Monitor or their designee immediately and closely monitor the subject for AEs/ SAE and laboratory abnormalities.

A subject suspected of overdose should be monitored until tazemetostat can no longer be detected systemically. For reference, five half-lives of tazemetostat would be at minimum 25 hours, longer in subject with delayed clearance. Decisions regarding dose interruptions or modifications will be made by the Investigator in consultation with the Medical Monitor or their designee based on the subject's clinical evaluation.

A plasma sample for PK analysis may be requested on a case-by-case basis. If requested, the plasma sample should be collected at least within 7 days from the date of the last dose of study treatment.

The quantity of the excess dose as well as the duration of the overdosing should be documented in the eCRF.

7 CONCOMITANT MEDICATIONS

Documentation of all concomitant medication administered during study treatment will be recorded in the eCRF at each visit.

Because there is a potential for interaction of tazemetostat with other concomitantly administered drugs through the cytochrome P450 system, over-the-counter medications, or alternative therapies must be recorded in the eCRF. The Investigator should be alerted if the subject is taking any agent known to affect or with the potential to affect selected CYP450 isoenzymes.

7.1 Permitted Medication(s)

- Supportive care measures and symptomatic treatment for any treatment-related toxicity, including short courses of glucocorticoids, if clinically indicated
- Glucocorticoids may be taken by subjects with CNS tumors, under the following conditions:
 - For control of neurological symptoms that may continue at a tapering dose
 - Intermittent use for control of nausea (not to exceed 0.3 mg/kg/dose dexamethasone, maximum of 20 mg) every 12 hours as needed
- Non-enzyme inducing anti-epileptic drugs
- Prophylactic use of standard anti-emetics
- Intermittent use of dexamethasone is permitted as an antiemetic (not to exceed 0.3 mg/kg/dose dexamethasone or maximum dose of 20 mg) every 12 hours as needed
- Blood and platelet transfusions, as needed per the judgment of the Investigator

7.2 Medications to be used with Caution

Substrates of P-gp, CYP3A, CYP2C8, CYP2C9, CYP2C19, and CYP2D6 should be used with caution. Medications that are substrates of CYP3A, CYP2C8, CYP2C9, CYP2C19, and CYP2D6, and have a narrow therapeutic range should be avoided if possible. Medications that are substrates of CYP2C8, CYP2C9, CYP2C19, CYP3A, and CYP2D6, and have a narrow therapeutic range include, but are not limited to, those listed in [Table 9](#), which follows.

NOTE: A listing of CYP inhibitors, inducers, and substrates can be found using the following link: <http://medicine.iupui.edu/clinpharm/ddis/table.aspx>

Table 9. Medications that are CYP3A, CYP2C8, CYP2C9, CYP2C19, and CYP2D6 Substrates that have a Narrow Therapeutic Range

CYP Enzymes	Substrates with Narrow Therapeutic Range
CYP2C8	Paclitaxel
CYP2C9	Warfarin, phenytoin
CYP2C19	S-mephenytoin
CYP3A	Alfentanil, astemizole, cisapride, cyclosporine, dihydroergotamine, ergotamine, fentanyl, pimozone, quinidine, sirolimus, tacrolimus,
CYP2D6	Thioridazine

Please refer to the following websites for a list of these medications or contact the Medical Monitor for additional questions:

<http://www.fda.gov/Drugs/DevelopmentApprovalProcess/DevelopmentResources/DrugInteractionsLabeling/ucm093664.htm>

7.3 Prohibited Medication(s)

- Antineoplastic therapy or other investigational therapy for the treatment of cancer
- Prophylactic use of hematopoietic colony stimulating factors

NOTE: Therapeutic use of hematopoietic colony stimulating factors is discouraged and should be discussed with the Medical Monitor and should be conducted according to the 2006 American Society for Clinical Oncology (ASCO) Guideline for use of white blood cell (WBC) growth factors [Smith, 2006].

- Treatment with strong inhibitors or strong inducers of CYP3A4 should not be taken within 14 days prior to first dose of study treatment and for the duration of study. Medications that are strong inhibitors and strong inducers include, but are not limited to those listed in Table 10, which follows.

Table 10. Medications that are Potent Inhibitors and Inducers of CYP3A4

CYP Enzymes	Strong Inducers	Strong Inhibitors
CYP3A	Avasimibe, carbamazepine, phenytoin, rifampin, St. John’s wort	Boceprevir, clarithromycin, conivaptan, grapefruit juice, indinavir, itraconazole, ketoconazole, lopinavir/ritonavir, mibefradil, nefazodone, nelfinavir, posaconazole, ritonavir, saquinavir, elaprevir, telithromycin, voriconazole

Please refer to the following websites for a comprehensive list of these medications or contact the Medical Monitor for additional questions:

<https://www.fda.gov/drugs/developmentapprovalprocess/developmentresources/druginteractions/abeling/ucm093664.htm#table3-3>

<http://medicine.iupui.edu/clinpharm/ddis/>

- Enzyme inducing anti-epileptic drug(s) (EIAED) including, but not limited to, carbamazepine, phenobarbital, phenytoin, and barbiturates, should not be taken within 14 days prior to the first dose of study treatment and for the duration of study treatment
- All herbal remedies and (including remedies in the form of herbal teas/infusions) are excluded while enrolled in the study
- Medicinal food supplements such as calcium, folic acid, vitamin D, multi-vitamin, etc., which have been taken under the advice from a physician, should be continued at the same dose and regimen during the study provided there are no contraindication as above. These should be listed as concomitant medications in the CRF.
- Any other supplements or alternative therapies should be discussed with the medical monitor prior to enrolment in the study or prior to initiating them during the study.

7.4 Non-Drug Therapies

Radiation Therapy: Palliative radiation therapy and potential concurrent dose interruptions will be permitted for pain or severe symptom control after discussion with the Medical Monitor. Radiation will be limited to non-target lesions only and documented in the eCRF.

Other palliative procedures: Other procedures intended for symptom control and potential concurrent dose interruptions may be permitted after discussion with the Medical Monitor. These procedures will be limited to non-target lesions only and documented in the eCRF.

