- Not Evaluable (NE): Cannot be classified by one of the five preceding definitions.

Notes:

- If LN(s) is documented as a target lesion(s) the short axis is added into the sum of the diameters (e.g. sum of diameters is the sum of the longest diameters for non-nodal lesions and the short axis for nodal lesions). When LN decrease to non-pathological size (short axis <10 mm) they should still have a measurement reported in order not to overstate progression.

- If at a given assessment time point all target lesions identified at baseline are not assessed, sum of the diameters cannot be calculated for purposes of assessing CR, PR, or SD, or for use as the nadir for future assessments. However, the sum of the diameters of the assessed lesions and the percent change from nadir should be calculated to ensure that progression has not been documented. If an assessment of PD cannot be made, the response assessment should be NE.
- All lesions (nodal and non-nodal) should have their measurements recorded even when very small (e.g., 2 mm). If lesions are present but too small to measure, 5 mm should be recorded and should contribute to the sum of the diameters, unless it is likely that the lesion has disappeared in which case 0 mm should be reported.
- If a lesion disappears and reappears at a subsequent time point it should continue to be measured. The response at the time when the lesion reappears will depend upon the status of the other lesions. For example, if the disease had reached a CR status then PD would be documented at the time of reappearance. However, if the response status was PR or SD, the diameter of the reappearing lesion should be added to the remaining diameters and response determined based on percent change from baseline and percent change from nadir.

Non-Target Lesion Evaluation

Assessment of non-target lesion(s) response is defined as:

- Complete Response (CR): The disappearance of all non-target lesions. All LN identified as a site of disease at baseline must be non-pathological (e.g., <10 mm short axis).
- Non-CR/Non-PD: The persistence of one or more non-target lesion(s) or lymph nodes identified as a site of disease at baseline ≥ 10 mm short axis.
- Progressive Disease (PD): Unequivocal progression of existing non-target lesions.
- Not Applicable (NA): No non-target lesions at baseline.
- Not Evaluable (NE): Cannot be classified by one of the four preceding definitions.

Notes:

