APPENDIX 5: RESPONSE ASSESSMENT IN NEURO-ONCOLOGY (RANO)

As discussed in (Wen, 2010).

Measurable disease is defined as bi-dimensionally contrast-enhancing or enhancing lesions with clearly defined margins by magnetic resonance imaging (MRI) scan, with 2 perpendicular diameters of at least 10 mm, visible on two or more axial slices that are preferably, at most, 5 mm apart with 0 mm skip.

Non-measurable disease is defined as either uni-dimensionally measurable lesions, masses with margins not clearly defined, or lesions with maximal perpendicular diameters less than 10 mm.

All measurable and non-measurable lesions must be assessed using the same techniques as at baseline.

Complete response (CR): Requires all of the following:

- complete disappearance of all enhancing measurable and non-measurable disease sustained for at least 4 weeks
- no new lesions
- stable or improved non-enhancing (T2/fluid-attenuated inversion recovery [FLAIR]) lesions
- subjects must be off corticosteroids (or on physiologic replacement doses only)
- stable or improved clinically

Note: Subjects with non-measurable disease only cannot have a CR; the best response possible is SD.

Partial response (PR): Requires all of the following:

- $\geq 50\%$ decrease compared with baseline, in the sum of products of perpendicular diameters of all measurable enhancing lesions sustained for at least 4 weeks
- no progression of non-measurable disease; no new lesions
- stable or improved non-enhancing (T2/FLAIR) lesions on same or lower dose of corticosteroids compared with baseline scan
- corticosteroid dose at the time of the scan evaluation should be no greater than the dose at time of baseline scan
- stable or improved clinically

Note: Subjects with non-measurable disease only cannot have a PR; the best response possible is SD.

Stable disease (SD): Requires all of the following:

- does not qualify for CR, PR, or progression
- stable non-enhancing (T2/FLAIR) lesions on same or lower dose of corticosteroids compared with baseline scan

In the event that the corticosteroid dose was increased for new symptoms and signs without confirmation of disease progression (PD) on neuro-imaging, and subsequent follow-up imaging shows that this increase in corticosteroids was required because of PD, the last scan considered to show SD will be the scan obtained when the corticosteroid dose was equivalent to the baseline dose.

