Appendix 1 provides additional detail for the interpretation of partial dates for medications.

13.3. CONCURRENT SURGERY AND PALLIATIVE RADIOTHERAPY

Concurrent anti-cancer surgery and palliative radiotherapy will be summarized for coded terms in the same manner as prior surgeries and prior radiotherapy. Concurrent anti-cancer surgery and palliative radiotherapy are those procedures that conclusively can be identified as occurring after the date of first dose of study drug up to, and including, the date of last dose of study drug.

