13.4. POST-TREATMENT ANTI-CANCER THERAPY AND RADIOTHERAPY

Post-treatment anti-cancer therapies will include anti-cancer therapies which started after discontinuation of study drug. The number and percentage of subjects with post-treatment anti-cancer therapy noted during survival follow up, as well as the incidence (number and percentage) of anti-cancer therapies by WHO Drug ATC level 4 and preferred drug name will be summarized. Post-treatment anti-cancer therapy will be listed for ITT population. Post-treatment radiotherapy will be listed together with prior and concomitant radiotherapies for ITT population.

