15.1. OBJECTIVE RESPONSE RATE AND DURATION OF RESPONSE

Best Overall Response (BOR)

The summaries of BOR will include number and percentage of subjects in each of these categories:

- Complete response (CR)

- Partial response (PR)
- Stable disease (SD)
- Progressive disease (PD)
- Not Evaluable (NE)
- Unknown/Missing

Confirmation of CR/PR is required at least 28 days after the initial CR/PR was first met. Subjects will be evaluated for response based on the following disease appropriate criteria:

- For CNS tumors, response will be assessed based on RANO (Wen PY, 2010).
- Solid tumors will be assessed based on RECIST version 1.1 (Eisenhauer EA, 2009).

Objective Response Rate

ORR is defined as the percentage of subjects achieving a confirmed CR or PR from the start of tazemetostat until PD or the start of subsequent anti-cancer therapy, whichever is earlier, according to the appropriate disease evaluation criteria.

Subjects with not evaluable, unknown or missing best response will be handled as non-responders, i.e. they will be included in the denominator when calculating the ORR.

For dose escalation, ORR (secondary endpoint) will be summarized by dose level and overall.

For dose expansion, ORR (primary endpoint) will be summarized by cohort and overall. An exact 95% binomial CI for ORR in each cohort and overall will be provided as well.

In addition, ORR will be summarized by dose level across the dose escalation and dose expansion phases and overall. For each dose level and overall, an exact 95% CI for ORR will be calculated.

Also, a subgroup analysis of ORR by prior radiotherapy (Yes vs No) will be performed for the expansion phase by cohort and overall, and for the entire study by dose level and overall.

A plot of the maximum percent tumor reduction from baseline in target lesions for each subject will be provided.

Duration of Response

DOR will be calculated only for subjects with a confirmed CR or PR. DOR is defined as the interval of time from the first documented evidence of confirmed CR or PR until the first

documented PD or death due to any cause, whichever occurs first.

DOR censoring rules will follow those of the PFS analysis defined in **Table 3** below.

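### On-study local therapy is limited to non-target lesions, a limit that the RANO appendix does not define, and no rule stops a RANO response first met after such therapy from counting towards ORR

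*Protocol*

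**What the plan says.** **Local therapy.** Protocol 7.4 allows palliative radiotherapy for pain or severe symptoms after discussion with the Medical Monitor, "limited to non-target lesions only and documented in the eCRF". Other palliative procedures carry the same limit: "These procedures will be limited to non-target lesions only and documented in the eCRF".

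**Response criteria.** CNS tumors are assessed by RANO (Appendix 5) and solid tumors by RECIST 1.1 (Appendix 4).
- RANO PR needs a fall of at least 50% "in the sum of products of perpendicular diameters of all measurable enhancing lesions sustained for at least 4 weeks". RANO CR needs all enhancing disease to be gone, measurable or not. Appendix 5 names no target or non-target lesions.
- SAP section 11 nevertheless describes RANO baseline burden by target lesions, non-target T1/Gd+ lesions and T2/FLAIR lesions.
- In RECIST, PR rests on target lesions. Non-target lesions count for CR ("Complete Response (CR): The disappearance of all non-target lesions") and for progression.

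**Window for ORR.** Protocol 14.4.1 and SAP 15.1 count confirmed responses from the start of treatment "until PD or the start of subsequent anti-cancer therapy, whichever is earlier".

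**SAP therapy classes.** For treatment up to the last dose, SAP 13.3 says: "Concurrent anti-cancer surgery and palliative radiotherapy will be summarized for coded terms in the same manner as prior surgeries and prior radiotherapy". For later treatment, SAP 13.4 says: "Post-treatment anti-cancer therapies will include anti-cancer therapies which started after discontinuation of study drug". It summarizes these by drug class and only lists post-treatment radiotherapy. SAP Tables 3 and 4 censor DOR and PFS at subsequent or new anti-cancer treatment, without saying whether radiotherapy or surgery qualifies.

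**The concern.** The expansion part is single-arm, and its primary endpoint depends on who is called a responder. If local treatment shrinks or removes a lesion that enters the response measure, and nothing excludes that response, the result is credited to tazemetostat. The bias runs towards activity.

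The plan already recognizes the issue for irradiated lesions, since SAP 3.2 adds an ORR subgroup by prior radiotherapy. Nothing equivalent covers radiotherapy or surgery during the study.

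The decision rule makes individual classifications matter. Protocol 14.2.1 asks for only three responders among 20 in each of Cohorts 1 to 3.

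**Working it through.** **1. Does the non-target limit protect a RANO response?** Take a subject with measurable enhancing lesions in two groups, with sums of products A (untreated) and B (treated locally). If A does not change and B is removed, the Appendix 5 sum falls by B/(A+B). That is at least 50% whenever B ≥ A. If B is smaller, local treatment still supplies part of the fall.
- Under Appendix 5 alone, the limit in Protocol 7.4 has no defined meaning, because no lesion is labelled non-target.
- If the SAP section 11 labels decide which lesions may be treated, but Appendix 5 decides the response, a measurable lesion labelled non-target can be treated and still count in the sum.
- If the section 11 labels also governed the response measure, the PR route would narrow. No text says that they do.

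**2. Does the window close?** ORR closes at progression or subsequent anti-cancer therapy. On-treatment local therapy sits in the concurrent class of SAP 13.3, separate from the post-treatment class of 13.4, and is linked to no efficacy rule. Protocol 7.3 prohibits antineoplastic therapy while 7.4 permits palliative radiotherapy, which points the same way. The natural reading is that the window stays open.

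**3. Does RECIST behave the same way?** From the Appendix 4 tables:
- Target CR with persisting non-target disease is already PR. Clearing the non-target disease makes it CR. ORR is CR + PR, so it does not change.
- Expansion requires measurable disease (Protocol 4.2.2), so this covers the RECIST-assessed expansion subjects.
- Unequivocal non-target growth is progression. Treating a growing non-target lesion can avert it and let a response survive to confirmation, which comes at 28 days or later. This is the only RECIST route into expansion ORR.
- Escalation admits evaluable disease (Protocol 4.2.1). With non-target disease alone, clearing it is a CR. There ORR is a secondary endpoint.

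**4. How sensitive is the decision rule?** Inputs from Protocol 14.2.1: n = 20, threshold 3, null 5%, alternative 20%; stated error rates 8% and 21%.
- Plan's figures: P(X ≥ 3 | 20, 0.05) = 1 − (0.3585 + 0.3774 + 0.1887) = 0.0755. P(X ≥ 3 | 20, 0.20) = 0.7939, so type II error is 0.2061. Both stated figures reproduce.
- One response wrongly credited, so the other 19 subjects need only two: P(X ≥ 2 | 19, 0.05) = 1 − (0.3774 + 0.3774) = 0.2453 from unrounded terms.
- A fraction q of true non-responders converted by local therapy, so that p = 0.05 + 0.95q (q is assumed; the documents give no rate):

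| q | p | P(X ≥ 3 of 20) |
|---|---|---|
| 1% | 0.0595 | 11.3% |
| 2% | 0.0690 | 15.6% |
| 5% | 0.0975 | 30.9% |

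**The case against.** The strongest reply is that the gap is one of definition and that the criteria carry other protections. New and subsequent anti-cancer treatment are undefined and not restricted to drugs. SAP 13.3 itself calls concurrent surgery anti-cancer, and 13.3 and 13.4 are tabulation sections, so a programmer could close the window or censor at local therapy. RANO CR and PR also require stable or improved clinical status and restrict corticosteroids. Responses must be confirmed, and radiotherapy is reserved for pain or severe symptoms, so many treated subjects would not qualify as responders.

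Much of this stands, and it limits the finding. A reader might infer four stronger claims that the documents do not support:
- **That local therapy never closes the ORR or PFS window.** The plan does not say so. Its categories only suggest it.
- **That clearing RECIST non-target lesions adds responders to expansion ORR.** It turns PR into CR and leaves ORR unchanged.
- **That every subject with CNS involvement is exposed through RANO.** RANO is assigned to CNS tumors, and Appendix 4 has its own brain-scan rules for CNS disease at baseline. The exposure of the primary endpoint is mainly Cohort 1.
- **That the type I error is 24.5%.** That figure assumes one false response has already occurred, and it would be the same for any misclassified response.

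The reply does not remove the mismatch between Protocol 7.4, Appendix 5 and SAP section 11. It also does not supply the missing counting rule. Clinical-status and steroid conditions make a locally produced response less likely but do not exclude it, since successful palliation can leave a subject clinically stable or improved.

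**Conclusion.** The point holds in a bounded form. For RANO-assessed subjects, mainly Cohort 1, the limit on local therapy does not match the response definition. As most naturally read, a response first met after local treatment of a contributing lesion counts as a drug response. For RECIST-assessed expansion subjects, the primary endpoint is exposed only through progression averted before confirmation.

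The size cannot be estimated, because no frequency of on-study radiotherapy or surgery is given. Conditional on one wrongly credited response in 20, the chance of passing at a true ORR of 5% is 24.5% instead of 7.5%. With an assumed 1% to 5% of non-responders converted, it is 11.3% to 30.9%. PFS and DOR can also be lengthened where local therapy averts progression, but these are secondary endpoints with no decision rule.

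The conclusion assumes that Appendix 5 governs RANO response and that the concurrent class is not subsequent therapy. If the SAP section 11 split also governs response, the PR route narrows.

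**What to change.** 1. **SAP 15.1.** Do not count a CR or PR first met after on-study or post-treatment radiotherapy or tumor surgery to a lesion that enters that determination. For RANO, this means any enhancing lesion used for that response. For RECIST, it means any target lesion and, for CR, any non-target lesion. A subject whose RECIST CR is set aside for a treated non-target lesion can still count as PR on untreated target lesions. Record which lesion was treated and when. This rule does not reach progression averted between first response and confirmation, but the record makes those cases visible.
2. **Lesion classes.** Reconcile Protocol 7.4, Appendix 5 and SAP section 11 on whether RANO has target and non-target lesions and which enter the response. This concerns how lesions are counted, not where palliative treatment is allowed.
3. **SAP Tables 3 and 4.** State whether radiotherapy and tumor surgery are new or subsequent anti-cancer treatment, and report PFS and DOR both with and without censoring at local therapy. Neither version is safe alone. A symptomatic lesion is often a progressing one, so censoring at its irradiation may be informative and can itself inflate PFS and DOR.

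The cost is SAP wording before database lock, a lesion identifier on the existing record of radiotherapy and procedures, one extra sensitivity table and possibly a slightly lower ORR.
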